2.5.4 Data and Safety Monitoring Committee

An independent Data and Safety Monitoring Board (DSMB) will be created to review this study. At periodic intervals (to be determined by the subcommittee) during the course of the study, the DSMB responsibilities are to:

1. Review the research protocol, informed consent documents and plans for data and safety monitoring;
2. Evaluate the progress of the study, including periodic assessments of data quality and timeliness, participant recruitment, accrual and retention, participant risk versus benefit, and other factors that can affect study outcome;
3. Consider factors external to the study when relevant information becomes available, such as scientific or therapeutic developments that may have an impact on the safety of the participants or the ethics of the study;
4. Review clinical center performance, make recommendations and assist in the resolution of problems reported by the PI;
5. Protect the safety of the study participants;
6. Report on the safety and progress of the study;
7. Make recommendations to the PI, IRB, and if required, to the FDA concerning continuation, termination or other modifications of the study based on the observed beneficial or adverse effects of the treatment under study;
8. Monitor the confidentiality of the study data and the results of monitoring;

9. Assist the PI by commenting on any problems with study conduct, enrollment, sample size and/or data collection.

The DSMB will include experts in neurosurgery or neurology, physical medicine and rehabilitation, occupational therapy, bioengineering, and biostatistics.

Members will consist of persons independent of the investigators who have no financial, scientific, or other conflict of interest with the study. Written documentation attesting to absence of conflict of interest will be required.

The University of Pittsburgh, Office of Clinical Research - Health Sciences will provide the logistical management and support of the DSMB. The Chairperson will be the contact person for serious adverse event reporting. Procedures for this will be discussed at the first meeting.

The core members of this research team will meet at least monthly to discuss study recruitment, study goals and progress, adverse events, participant complaints, modifications, and confidentiality of ongoing studies. The investigators and study team will ensure that proper procedures are in place to ensure data integrity and participant safety. Data will be reviewed and any possible study design changes resulting from our experience or external studies/publications will be discussed. Our priority is to maintain participant safety and confidentiality while collecting data that accurately demonstrates the efficacy of using the NeuroPort Arrays as a direct brain interface. We will comply with the IRB's policy for the reporting of serious and unexpected adverse events as described in Chapter 3.0 of the University of Pittsburgh's IRB Reference Manual. Similarly, we will report adverse device events to the FDA in accordance with the agency's expedited reporting requirements. The outcomes of these meetings will be summarized and included in the annual IRB continuing review. Minutes for these meetings will be kept on file.

3.0 Clinical Protocol For Extension Study

3.1 Title of clinical protocol

Long-Term Microelectrode Brain-Machine Interface (Extension Study)

3.1.1 Protocol number

University of Pittsburgh, PRO12090216

3.1.2 Version number and date

Version 6, January 14, 2013 (Expiration Date: 10/7/2014)

3.2 Study design

3.2.1 General study design

This study is an extension to a prospective, non-randomized, open-label feasibility study that will be conducted at the University of Pittsburgh.

3.2.2 Study design schematic

Figure 2 illustrates the proposed study design for the core study. For the extension study, the Experimental Procedures section (BMI testing, wound checks, clinical exams, etc.) would be expanded from 1 year in duration to up to 5 years. The explant surgery and follow-up visits would continue as described in Figure 2 after the extended implantation period.

3.3 Subject selection

3.3.1 General characteristics of the proposed subject populations(s)

Participants who participated in the core study (IDE G100298, University of Pittsburgh PRO10080021) may be eligible for the extension study if they have had positive clinical and research outcomes after 6 months of implantation and meet the eligibility criteria described in Sections 3.3.3 and 3.3.4.

3.3.2 Anticipated number of research subjects

Up to 5.

3.3.3 Inclusion criteria

- 1) Participant in PRO10080021 study (IDE G100298) who is at least 6 months post-implant
- 2) Have no unresolved significant adverse events during participation in PRO10080021
- 3) Have demonstrated at least 4-dimensional control of a virtual or real robotic arm during participation in PRO10080021
- 4) Have a stable psychosocial support and caregivers who are able to perform the necessary daily care of the participant's skin and pedestal site; This requires that the subject identify a caregiver and a back up who have been in place for greater than 6 months and are able to provide needed physical and psychosocial support. This will be assessed by the study PI and neurosurgeon.
- 5) Age 18-70 years old at the time of consent and planned explant
- 6) Have a life expectancy greater than 12 months as assessed by the study principal investigator and neurosurgeon sub-investigator
- 7) Live within 1 hour of the University of Pittsburgh, or be willing to travel there, once per week for BMI testing
- 8) Interested in having the NeuroPort arrays remain in place for 6 months to 4 years beyond the 1 year implantation that is part of PRO10080021. Participants can

decide to extend the implantation for any duration between 6 months and 4 years. This can be decided at any point during the study.

- 9) Participation is not expected to have an adverse effect on mental well-being as judged by the rehabilitation psychologist
- 10) Documentation of informed consent is obtained from the participant or their legal representative

3.3.4 Exclusion criteria

- 1) Women of childbearing age who are pregnant, lactating, or plan to become pregnant during the next 60 months
- 2) Development of any medical condition that would put the participant at increased clinical risk during extended implantation

3.4 Study procedures

3.4.1 Screening procedures

Participants must already been enrolled in PRO10080021 to be eligible. They will meet with one of the physicians on the study (PI or neurosurgeon) to discuss the study procedures and risks of the proposed study. Informed consent will be obtained by the study PI after these discussions to ensure that the participant has time to review the consent form. As in the core study, a family member or caregiver will also sign the consent form acknowledging that they will support the participant as described in the protocol. It is the responsibility of the principal investigator (PI) that each subject being considered for participation in the study be given a full explanation of the protocol. Informed consent is mandatory after adequate explanation of the objectives, methods, anticipated benefits, and potential risks of the study before any study specific procedures are performed. The informed consent form must include the required eight basic elements. Informed consent will, consistent with site institutional policies and FDA regulations (21CFR, Part 50), be obtained in the following manner.

Participants will already have the NeuroPort Arrays implanted for at least 6 months before being approached about the extension study so they will be very familiar with the study procedures and risks. The study PI will inform the participant and their family or caregiver about the study procedures and risks for the extension study. During a separate meeting, after the subject has had time to review the consent, an investigator will meet with them to review any additional questions. Because the device will be utilized in the subject's chronic care environment, which may be the subject's home, an understanding of the requirements of participation is important to the subject as well as a committed family member and/or caregiver. If the subject is interested in participating, the consent will be completed by the subject, a family member or primary caregiver, and the study PI. After completion of the consent, participation in the study is initiated. As part of screening, the subject will complete a evaluation by the rehabilitation psychologist to document that participation in an extended duration study is not expected to have any adverse

effect on the participant's well being and that they understand the limited duration of the extension study (up to 5 years post-implant) and the risk that their performance in BMI related activity may degrade over time. All of these interactions between the subject and study personnel will serve to further educate the subject. The subject may withdraw at any time.

After consent, eligibility criteria will be verified by self-report, using data from PRO10080021, checking the participant's medical records as necessary, or via interview as described below.

(1) Psychology interview: The rehabilitation psychologist will provide independent determination of eligibility on the basis that the participant understands the study procedures and limited duration. The psychologist will give a recommendation of "eligible" if they believe that participation in the extension study will have no adverse effect on the participant's mental well-being.

3.4.2 Experimental procedures

This study is an optional extension to PRO10080021. Consent and screening for this study may occur as early as 6 months after implant and up to 13 months after implant (the maximum duration allowed in the original protocol). BMI testing will occur as described in the original protocol with similar ongoing clinical monitoring and follow-up as described below:

Brain-Machine Interface (BMI) Training/Testing:

Neural recording will be conducted for the duration of implantation. The recorded neural data will be used to operate a BMI system that allows the participant to control a computer cursor, virtual object, or assistive device. While the NeuroPort Arrays are implanted, we will conduct BMI training for up to 8 hours per day for up to 5 days per week. At least 1 session per week will be attempted while the array is implanted. BMI testing may occur at the University of Pittsburgh, UPMC, or in the participant's home. Rest, meals, and other breaks will be scheduled as needed. We may not conduct training sessions every day. This will be determined by the research staff and the subject. Also, we may not conduct testing sessions for up to 8 weeks per year. Since participants will have already completed 1 year of testing, we hope to minimize the burden on participants while still collecting valuable data related to signal quality and BMI control. The subject will go no longer than 3 weeks between testing sessions. This will assure that the study team can continue to monitor the wound site and well being of the participant.

At the beginning of each BMI testing session, an investigator will connect the Patient Cable to the Patient Pedestal. We may also record neural activity using EEG electrodes which are placed on the scalp in order to measure larger networks of brain activation. There are two types of behavioral tasks that the subject will participate in as part of the BMI training/testing: 1. Open-loop and 2. Closed Loop. These tasks are the same as described in Section 2.4.2.

Neural and behavioral data will be recorded during each BMI session in order to address the Specific Aims. As described in Section 2.4.2, we will track neural data, including the number of single units and the average firing rate over the duration of the implant. Behavioral data may include kinematics of a cursor, virtual object, robotic arm, etc. We will also compute the success rate achieved by the participant for a given task over a number of sessions. Impedance measurements will be collected during BMI testing sessions throughout the study. We will also document volunteered or observed adverse events at least weekly as part of the BMI training sessions as a measure of device safety. Subject may be asked at test sessions about level of fatigue, quality of sleep at home or other factors that may affect quality of testing performance.

At the end of each session, an investigator will remove the Patient Cable and clean the device. At a minimum, the Patient Pedestal should be cleaned every 7 days by a family member, caregiver, medical professional, or study team member. We will provide detailed cleaning instructions to the participant and anyone who may assist with the cleaning. We will monitor the subject's temperature on days that BMI testing occurs as this can be an early indicator of infection. In addition, we will instruct the subject to monitor and record their own temperature daily as well. A family member or caregiver will be asked to inspect the Patient Pedestal sites on a daily basis to identify any changes that may indicate an infection such as erythema, drainage, ecchymosis, pain, or unusual redness along the lead tunnel or pedestal. The study neurosurgeon and PI will train the research team and family member or caregiver in how to monitor wound healing.

Sleep Diary:

We may ask the participant to maintain a sleep diary which measures the amount and quality of sleep each night.

In-Home Sleep Evaluation:

An in-home sleep evaluation may be performed to evaluate how sleep, or lack of sleep, impacts a participant's performance with the neuroprosthetic device. We may measure the participant's brain activity during sleep (in their home) using EEG and/or intracortical recordings from the NeuroPort electrodes. This testing may be completed by a study team member in the subject's home, or in the case of EEG monitoring, it could be conducted by the subject and a caregiver once the electrodes are setup by a study team member. In addition to brain activity, we may record additional physiological information including electrocardiogram (EKG) activity, temperature (using a small sensor near the nose), and respiration (using elastic belts around the chest and abdomen). We will plan to set up the equipment early enough so as not to interfere with their normal sleep routine. The equipment will be removed after their normal wake-up time. We may ask the subject to perform simple BMI tasks before and after periods of normal sleep. Our goal is to determine how normal sleep (including normally occurring variations in sleep quantity and quality) affects neural activity and BMI performance.

Ongoing Clinical Evaluations:

A clinical investigator will perform a monthly clinical evaluation to monitor the participant's neurological and musculoskeletal status. Wound checks will also be performed at this visit. If any changes in neurological status or musculoskeletal functioning are noted, appropriate medical care will be provided. These clinical visits will likely be combined with research visits to the University of Pittsburgh or UPMC.

Ongoing Psychological Evaluations:

The subject will have opportunities to talk to a psychologist throughout the study, either over the phone or in person. These discussions will be scheduled regularly (approximately every 3 months) to discuss any concerns the subject may have. The psychologist may refer the subject for additional meetings as necessary. In addition, physician-investigators, including the study PI and neurosurgeon, will be interacting with the subject on a regular basis and can refer the subject to a psychologist at their discretion. If the subject has severe problems or concerns, he or she may be withdrawn from the study.

Imaging:

The study neurosurgeon may order a head x-ray or CT if there is a change in the patient's neurological examination or the patient experiences severe headaches, nausea, and/or abnormal behavior. These procedures will enable our neurosurgeon and their clinical team to identify infection, bleeding, edema, or neurological dysfunctions as early as possible and treat them properly. These imaging procedures will take place in UPMC facilities.

Removal of the electrodes:

Subjects will undergo a second surgery at UPMC Presbyterian Hospital approximately 5 years after implantation of the NeuroPort Arrays. It is possible that the NeuroPort Arrays may be explanted earlier due to technical problems, clinical complications, investigator-initiated withdrawal, or subject-initiated withdrawal. The participant will go through standard preoperative screening procedures which may include a blood draw. Explantation procedures are the same as described in Section 2.4.2.

Post-operative care:

Post-operative care will depend on the participant's condition. The participant will remain in the post anesthesia care unit (PACU) for approximately 3 hours after surgery. They will be transferred to the neurosurgical intensive care unit (ICU) for approximately 24 hours before transitioning to the neurosurgical medical surgery recovery unit where they will stay for 1-2 days. The PACU, ICU, and medical surgery recovery unit are all located at UPMC Presbyterian Hospital. Post-operative imaging may be requested by the study neurosurgeon depending on the

participant's condition. The participants will then stay at the UPMC Rehabilitation Institute for up to 3 days for post-operative rehabilitation. The rehabilitation stay serves primarily to ensure that the participant is ready to resume normal daily activities while medical staff can monitor wound healing. The study neurosurgeon, PI and rehabilitation team will determine when the participant will be discharged and sent home.

3.4.3 Follow-up procedures

Post-surgical MEG testing:

We will ask the subject to come back for up to 3 MEG sessions within 6 months after completion of the BMI training. The follow-up MEG sessions are optional visits for the subjects. If the subject is interested in participating, we will plan to schedule the visits at 2 weeks, 6 weeks, and 3 months after the explantation surgery. The same tasks that were completed during the pre-surgical MEG session will be repeated. In addition to measuring changes in single unit activity over the duration of the study, the MEG studies will allow us to determine if plasticity was induced due to BMI training in terms of volitional modulation of motor cortex activity. These visits are expected to last up to 2 hours each.

Clinical follow-up:

Follow-up visits will be scheduled in order to ensure that the bone flap and Patient Pedestal sites are healing properly. These visits will be scheduled at the discretion of the study neurosurgeon and the subject. We expect that each subject will have two follow-up visits with the study neurosurgeon and their clinical team at 1 and 4 weeks (+/- 3 days) after explantation. Depending on the healing process of the implantation site and percutaneous port, additional imaging studies (x-ray, CT scan, or MRI) may be performed although this is unlikely.

Post-explant counseling:

Subjects will be scheduled for an appointment with a licensed rehabilitation psychologist to assure that they have an opportunity to discuss any concerns they may have post explantation.

3.4.4 Study compliance and withdrawal:

The subject will be under medical supervision for the duration of this study. Their health will be the top priority and participation will be discontinued if surgical intervention is required. The study neurosurgeon and PI will be primarily responsible for evaluating the subject's condition. Complications that could result in removal from the study (and having the NeuroPort Array removed) include:

- Treatment resistant (serious) infection at the implantation site or Patient pedestal
- Array technical malfunction resulting in an inability to collect data that is useful

for brain-control tasks

- Serious medical complications that compromise the subject's safety or health
- Psychological distress associated with decrements in performance or continued implantation.

If the participant is non-compliant (e.g., unwilling to participate in BMI training sessions) they may be withdrawn from the study. The NeuroPort Arrays will be explanted and they will be strongly encouraged to attend the follow-up monitoring visit with the study neurosurgeon.

3.4.5 Schedule of activities (Study Table):

The schedule of activities remains the same as in Table 1, Section 2.4.5, except that the implantation duration and all affiliated procedures (BMI testing, psychological evaluations, clinical exams, etc.) may be extended for up to 5 years post-implant.

3.5 Study outcome evaluations

3.5.1 Study endpoints

The NeuroPort Arrays will be removed up to 5 years after implantation. A participant will be considered a success for safety if the device is not explanted for safety reasons during the 5 year post-implant evaluation. If the subject experiences treatment resistant (serious) adverse events, he or she will be withdrawn and the arrays will be explanted early (See Section E 3.4.4). The study may also end early if the subject is non-compliant (See Section E 3.4.4).

If the participant wishes to leave the NeuroPort Array implanted after 5 years, the participant will be counseled that they should have the NeuroPort Array removed and that not doing so could result in clinically significant adverse events. They will also be informed that brain-machine interface training will not continue. The consent form includes a statement that participants will be financially liable for any medical care resulting from complications of not having the device removed upon instruction of the study PI. We will however allow participants to have the device removed at anytime and the explantation costs would be covered by this study.

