Specific Aim 3: Source localization (combining the MEG and structural MRI data) will be used to identify the anatomical foci of cortical activation controlling imagined and/or attempted movement. The coordinates (x,y,z) of the center of activation can be computed with fMRI or MEG relative to the head coordinate system defined using bony landmarks. The location and area of cortical activation measured by fMRI and MEG during imagined and/or attempted movement will be compared for each subject. A paired t-test will be used to compare location and area of cortical activation measured by the two imaging techniques using data from all participants, although the power of this test may be limited by sample size. Qualitative comparisons will be informative and we expect agreement between the two imaging techniques in terms of localizing the area for array implantation. MEG potentially offers additional information due to higher temporal resolution.

Specific Aim 3a: Cortical modulation will be calculated as the power of the 4-40 Hz frequency band of MEG data that is recorded during imagined and/or attempted movement. Specific Aim 3a will be evaluated by applying repeated measures ANOVA to test for differences in modulation (magnitude and total area) during imagined and/or attempted movement during the pre-surgical procedures and the follow-up sessions.

Specific Aim 4: Sleep quality measures will be correlated to BMI performance on the following day while controlling for differences in task difficulty. Linear regression will be used to determine the most predictive sleep quality metrics.

The study will be considered a success if the device is not explanted for safety reasons during the 12-month to 5 year post-implant evaluation. This study is not being proposed to support marketing applications (510(k) or PMA) for the NeuroPort Arrays. Instead, the goal is to demonstrate that three-dimensional microelectrode arrays provide a safe way to record sufficient neural information for controlling complex assistive devices that will increase the independence of individuals with disabilities.

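### Extension participants may elect any implant duration from 1.5 to 5 years, but the 5-year safety rule has no minimum follow-up or censoring, so an elective 18-month completer scores as a success

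*Combined protocol and SAP*

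**What the plan says.** The extension sections describe the implant period and the safety horizon in four places.

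- **Section 3.3.3, item 8.** Participants must be interested in having the arrays "remain in place for 6 months to 4 years beyond the 1 year implantation that is part of PRO10080021". They may "decide to extend the implantation for any duration between 6 months and 4 years", and "This can be decided at any point during the study".
- **Section 3.3.3, item 5.** The age condition is "Age 18-70 years old at the time of consent and planned explant".
- **Section 3.4.2, removal of the electrodes.** The second surgery takes place "approximately 5 years after implantation of the NeuroPort Arrays", with earlier removal possible for technical problems, complications or withdrawal.
- **Section 3.5.1.** "The NeuroPort Arrays will be removed up to 5 years after implantation". A participant is a safety success if "the device is not explanted for safety reasons during the 5 year post-implant evaluation". Removal on request is allowed at any time.

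Section 3.5.3 then defines success for the study as the device being "not explanted for safety reasons during the 12-month to 5 year post-implant evaluation".

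By contrast, the core study (Section 2.5.1) removes the arrays at 1 year, give or take 30 days, and scores safety over 12 months. There the implant period and the endpoint match.

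**The concern.** The extension carries over the form of the core endpoint and puts 5 years in place of 12 months, but makes the implant duration elective. Success is defined only by the absence of an explant for safety reasons. A planned removal at 18 months is not such an explant, so the rule as written scores it as a success. The same would apply to a removal for technical failure or non-compliance. These sections plan no censoring, no time-to-event summary and no rate per unit of exposure.

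The extension exists to learn about years 1 to 5 after implant. Section 4.1 states the belief that longer implantation adds neither chronic implantation risk nor fibrosis risk, and accepts that infection risk at the pedestal continues after surgical healing. Only observed late follow-up can test those beliefs. A success count that gives 1.5 years the same credit as 5 years cannot, and the shorter the elected durations, the better the device appears.

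**Working it through.** The plan gives no target rate, power or expected safety-explant risk, so there is no figure of its own to reproduce.

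**1. Range of planned durations (Section 3.3.3, item 8).** Shortest: 1 + 0.5 = 1.5 years. Longest: 1 + 4 = 5 years. An 18-month completer contributes 1.5 / 5 = 30% of the 5-year exposure. Counting only time after month 12, the share is 0.5 / 4 = 12.5%.

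**2. Effect of the age limit (item 5).** Planned explant must fall by age 70, and 70 − 5 = 65. Core entry is open to age 70, so anyone implanted after about 65 can join the extension only with a planned duration below 5 years. Some short durations are therefore built in.

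**3. The rule applied to an elective 18-month removal.**

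| Place | Horizon | Scoring of elective removal at 18 months |
|---|---|---|
| 3.3.3 item 8 | 1.5 to 5 years, participant's choice | A completed duration |
| 3.4.2 | About 5 years | Not stated |
| 3.5.1 | Up to 5 years for removal; 5-year evaluation for success | Success, because not a safety explant |
| 3.5.3 | 12 months to 5 years | No safety explant; shorter follow-up not addressed |

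**4. Scale.** Assumptions, none taken from the documents: constant hazard of safety explant from implant; true 5-year risk F; 5 independent participants, none with a safety explant by 12 months. Conditioning on 12 months suits a group that is already at least 6 months post-implant at entry.

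With h = −ln(1 − F)/5, the chance that all 5 are free of safety explant from year 1 to year t is exp[−5h(t − 1)] = (1 − F)^(t − 1).

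- All leave at 18 months: (1 − F)^0.5.
- All followed to 5 years: (1 − F)^4.

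| Assumed F | All leave at 18 months | All followed to 5 years |
|---|---|---|
| 5% | 0.95^0.5 = 97% | 0.95^4 = 81% |
| 10% | 0.90^0.5 = 95% | 0.90^4 = 66% |
| 20% | 0.80^0.5 = 89% | 0.80^4 = 41% |
| 40% | 0.60^0.5 = 77% | 0.60^4 = 13% |

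For a mixed group at F = 20% (two leave at 1.5 years, one at 3, two at 5), the years after month 12 total 2 × 0.5 + 2 + 2 × 4 = 11. The chance is 0.8^(11/5) = 61%.

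**5. Sensitivity to hazard shape.** Take a declining hazard (Weibull, shape 0.5) with the same 20% risk at 5 years. Cumulative hazard is H(t) = 0.2231 × (t/5)^0.5, so H(1) = 0.0998, H(1.5) = 0.1222 and H(5) = 0.2231. Conditional on 12 months, the chance that all 5 succeed is exp[−5 × 0.0224] = 89% at 18 months and exp[−5 × 0.1233] = 54% at 5 years. The gap falls from 48 to 35 percentage points.

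**6. What zero events would show.** With no safety explants, the one-sided 95% upper bound on the rate is −ln(0.05) / person-years. Five participants followed 5 years from implant give 25 person-years and a bound of 0.12 per year, or a 5-year risk of 1 − exp(−5 × 0.12) = 45%. Five 18-month completers give 7.5 person-years and 0.40 per year, or 86%. Treating those five as 0 of 5 failures at 5 years gives an exact binomial bound of 1 − 0.05^(1/5) = 45%, which their follow-up does not support.

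**The case against.** The strongest reply is that 5 years is a ceiling, not a fixed horizon. The removal sentence in Section 3.5.1, the schedule in Section 3.4.5 and the range in Section 3.5.3 can all be read that way, and no section says that an 18-month completer is a 5-year success. That is correct: the scoring follows from the literal rule and from the absence of any other. But the ceiling reading still does not say how shorter follow-up is scored, and it sits poorly with Section 3.4.2.

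A second reply is that no pooled success proportion, interval or test is planned. There are at most 5 participants, the core study uses single-subject analyses, and the work is not meant to support a marketing application. This stands, and it limits the practical weight. A reader might infer that the plan will report an inflated 5-year success percentage; the documents do not support that.

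A third reply concerns the arithmetic. Section 4.1 places most of the infection risk in the operating room, which argues for an early, declining hazard. The direction of the gap survives, but its size does not.

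Finally, because the end date may be chosen late, a reader might infer that a participant with an emerging problem could elect to finish before a safety explant is declared. The documents give no sign that this would happen. Adverse effects are recorded whatever their cause (Section 4.2.3), assessed by the investigator-sponsor (Section 4.2.3.2), and local wound problems go to the DSMB chair within 24 hours (Section 4.2.5). Nothing classes a removal requested because of a complication as non-safety.

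**Conclusion.** The point holds as a mismatch between an elective implant duration and a 5-year success rule with no minimum follow-up or censoring. Under the wording of Section 3.5.1, an elective 18-month completer is a success with 30% of the 5-year exposure. Sections 3.3.3, 3.4.2, 3.5.1 and 3.5.3 word the horizon differently and must be reconciled. Which removal time is right is not a question for this review.

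The 89% against 41% is an illustration. It rests on an assumed 20% risk, a constant hazard, survival to 12 months without safety explant, and the extreme case in which all 5 leave at 18 months. Mixed durations or a declining hazard give a smaller gap. For a feasibility study of at most 5 this is a correction worth making before reporting. It is not a flaw in the conduct of the study, and it gives no ground for restricting the participants' choice of duration.

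**What to change.** In Sections 3.5.1 and 3.5.3, use one definition: freedom from safety explant over the participant's actual implanted time. Then:

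- treat a completed elective duration as censored at removal, not as a 5-year success;
- list each participant's implant duration and reason for explant, with any device-related event unresolved at removal;
- report safety explants per implant-year;
- reconcile the horizon wording across Sections 3.3.3, 3.4.2, 3.5.1 and 3.5.3.

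Any fixed-time figure should come from a censoring-based estimate such as Kaplan-Meier. Proportions restricted to those who reached a landmark or had an earlier safety explant should be avoided. They keep early events but drop event-free elective completers, and so overstate risk. With a constant hazard from implant, a 20% 5-year risk and durations uniform on 1.5 to 5 years, such a proportion shows 81.6% success at 3 years against a true 0.8^(3/5) = 87.5%.

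The cost is a few sentences, one listing and a short record at removal, with no new visits. The downside is that fewer participants can support a 5-year statement.
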